volunteers will be blinded to the conditions. During each session, volunteers will first perform a task training and a short (approx. 5 min) block of the approach/avoidance task (Ap/Av) without TMS to record intrinsic EEG activity and use it for calibrating the real-time TMS-EEG system (Shrinpour et al., 2020). Then, volunteers will perform 8 main blocks of approach/avoidance tasks with TMS (approx. 6 minutes per block) in randomized order: 1. congruent task + TMS at theta peaks, 2. congruent task + TMS at theta troughs, 3. incongruent task + TMS at theta peaks, and 4. incongruent task + TMS at theta troughs. During each task trial, the volunteer will receive a single burst of TMS (up to three pulses) at the peak or trough of ongoing theta rhythm. In the verum TMS-EEG condition/block, we will apply TMS pulses over the left DLPFC based on the left DLPFC theta oscillations. In the sham condition/block, TMS will be applied over the head vertex (which should not induce changes in the prefrontal activity but will induce the same sensory effects). EEG will be recorded throughout the TMS-EEG sessions. In addition, electrooculography and heart rate will be recorded together with EEG using non-invasive sensors for the accurate removal of ocular and cardiac artifacts. There will be 3-5 min breaks in-between the blocks for rest. The total number of TMS pulses per day will not exceed 3,000 pulses, many times lower than the established safety limit of 90,000 pulses per day (Cole et al., 2022, 2020).

[figure not shown]

Diagram 1: Experimental pipeline with timing.

5.2. Study Procedures:

5.2.1. Initial questionnaires: during the initial visit, each volunteer will fill out standardized self-reported questionnaires regarding their demographic data and emotional assessment. These include the Patient Health Questionnaire (PHQ-9), General Anxiety Disorder (GAD-7) tool, and Quick Inventory of Depressive Symptomatology – Self-Rated (QIDS-SR-16). Total time necessary to complete all questionnaires is approx. 25 minutes.

5.2.2. MRI: During the first session, 3T MRI scans will be performed at the Center for Magnetic Resonance Research (CMRR). Participants will

MEDICAL PROTOCOL (HRP-590)

PROTOCOL TITLE: Investigating the causal and phase-dependent role of prefrontal theta oscillations in approach/avoidance behavior

VERSION DATE: 14/09/2024

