- 15.1. Data Analysis Plan: We will analyze reaction times from the Ap/Av test using Hierarchical Bayesian Drift Diffusion Models (HDDM). This model is optimal for two alternative forced-choice cognitive tasks. It estimates single-trial performance in the presence of various sources of noise and trial-by-trial variations. The model will take reaction times as inputs and recover the variables of interest – speed of evidence accumulation (drift rate) and the decision thresholds for responding to the stimuli of positive and negative valence.

EEG from the stimulation and task periods will first be preprocessed. We will exclude noisy trials and interpolate noise channels, bandpass filter the signals (0.2-80 Hz) using Butterworth noncausal filters, suppress the line noise, and clean the data with extended InfoMax ICA. After preprocessing and artifact suppression, we will epoch the data around the TMS pulses, and calculate the TMS-evoked potentials in the left DLPFC caused by the stimulation at the peak and trough of theta oscillations.

- 15.2. Power Analysis: We estimated that medium effect size of Cohen's $d = 0.5$, which was observed in comparable studies (Shirinpour et al., 2020; Gordon et al., 2022), will be reached with a sample size of 26 volunteers.

- 15.3. Statistical Analysis: The HDDM parameters will be compared between the conditions using Generalized Linear Mixed-Effect Models (GLMM) with model outcomes as dependent variables, stimulation conditions (real vs control and peaks vs trough) as categorical independent variables, and participant IDs as a nuance variable. Further, post-hoc pairwise nonparametric tests will be applied between the conditions. Latency and magnitude of TMS-evoked potentials (TEPs) will be compared between the conditions using nonparametric cluster-based permutation test with false discovery rate correction for number of comparisons. Outcomes of TEPs and behavioral analysis will be correlated using Spearman statistics.

- 15.4. Data Integrity: Raw data and corresponding log files will be examined by the principal investigator on a regular basis during the data collection stage. The automatic log files will be generated automatically by the software which runs the EEG amplifier. The log files will be cross-checked

MEDICAL PROTOCOL (HRP-590)

PROTOCOL TITLE: Investigating the causal and phase-dependent role of prefrontal theta oscillations in approach/avoidance behavior

VERSION DATE: 14/09/2024

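### Section 15.3 gives the mixed model one participant term and does not fix its error term; if site or phase effects differ between people, the main-effect error rate can drift from 5% in either direction.

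*Combined protocol and SAP*

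**What the plan says.** Section 15.3 is the only place that specifies the behavioural model. "The HDDM parameters will be compared between the conditions using Generalized Linear Mixed-Effect Models (GLMM) with model outcomes as dependent variables". The predictors and the participant term are given as "stimulation conditions (real vs control and peaks vs trough) as categorical independent variables, and participant IDs as a nuance variable". The section does not say whether the participant term is fixed or random, or whether it is an intercept alone or includes slopes. It does not give the number of rows per person or the coefficient that carries the primary test, and it names no site-by-phase interaction.

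The parameters come from section 15.1: "speed of evidence accumulation (drift rate) and the decision thresholds for responding to the stimuli of positive and negative valence". The design is fully within-person. In section 5.1, "volunteers will perform 8 main blocks of approach/avoidance tasks with TMS (approx. 6 minutes per block) in randomized order", and section 18.3 confirms that each participant experiences all procedures. Section 3.1 makes the peak-versus-trough comparison of reaction times the primary endpoint. Section 5.2.3 adds the congruent–incongruent reaction-time difference as a primary test outcome.

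**The concern.** A single participant term removes differences in overall level between people. It does not let the peak–trough or DLPFC–vertex difference itself vary from person to person. When a person contributes several values per condition, that variation is the noise against which an average effect should be judged, with 26 − 1 = 25 degrees of freedom. A model without it tests against a pooled residual with many more degrees of freedom.

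Several values per cell are a likely reading. Section 15.1 estimates parameters by valence, and section 5.2.3 needs the two task rules kept apart. If effects do vary, intervals for site and phase can be too narrow and a chance result in the main behavioural comparison more likely than 5%. This would occur even with perfectly measured parameters.

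**Working it through.** The plan gives no figure for this point, so there is none to reproduce.

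**Inputs from the protocol.** n = 26 (15.2); 2 sites × 2 phases (15.3); 8 blocks (5.1, 5.2.5), read as 2 sites × 2 phases × 2 task rules; 2 valences (15.1). Section 5.2.3 still describes four blocks; I use eight. One parameter then gives 4 rows per person (site × phase), 8 (also split by valence or task rule) or 16 (split by both), so m = 1, 2 or 4 rows per cell.

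**Assumptions.** Two-sided α = 0.05; residual SD 1; SD of the person-specific site and phase differences τ = 0.5 or 1.0. The documents give none of these. Parameter estimates are treated as independent given the person.

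**Formulas (balanced data, participant intercept only).** Residual df = 4nm − n − 3. Expected residual mean square E = 1 + (n − 1)·m·(sum of the slope variances)/df. True variance of an average effect divided by the variance the model assumes: R = (1 + mτ²)/E. Type I error = P(|t| > t₀.₉₇₅/√R), and relative interval width = 1/√R.

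**Worked case, m = 2, τ = 0.5.** df = 208 − 29 = 179. E = 1 + 25 × 2 × (0.25 + 0.25)/179 = 1.140. R = 1.5/1.140 = 1.316, √R = 1.147. 1.973/1.147 = 1.720, which gives 8.7%.

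| Rows per person | τ | df | E | R | Main-effect type I error | Same, if the interaction varies equally |
|---|---|---|---|---|---|---|
| 4 | 0.5 | 75 | 1.167 | 1.071 | 5.8% | 5.0% |
| 4 | 1.0 | 75 | 1.667 | 1.200 | 7.3% | 5.0% |
| 8 | 0.5 | 179 | 1.140 | 1.316 | 8.7% | 7.8% |
| 8 | 1.0 | 179 | 1.559 | 1.925 | 15.7% | 12.4% |
| 16 | 0.5 | 387 | 1.129 | 1.771 | 14.0% | 13.0% |
| 16 | 1.0 | 387 | 1.517 | 3.296 | 28.0% | 24.2% |

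Simulation with 20,000 null data sets per setting agrees. With no interaction variance, the site and phase tests reject in 5.9–7.6% (4 rows), 8.3–15.5% (8) and 13.9–28.5% (16). With no variation in effects at all, the rate is 4.8–5.2%. Interval widths in the sixth column's settings run from 1/√1.071 = 0.97 to 1/√3.296 = 0.55 of the correct width.

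**Site × phase.** With no person-to-person variation in the interaction, the numerator of R is 1 and the test is conservative (1.1–3.8% simulated when both main effects vary with SD 0.5 or 1.0). If the interaction varies as much as the main effects, it rejects in about 5% with 4 rows, 7.9–12.5% with 8 and 13.2–24.4% with 16.

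**Valence and task rule left out of the model.** Each omitted effect of δ residual SDs adds N(δ²/4)/df to E, where N is the total number of rows. For δ = 2, this adds 208 × 1/179 = 1.162 with 8 rows (one factor) and 416 × 2/387 = 2.150 with 16 rows (two factors).

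| Rows | δ | Type I error, τ = 0.5 | Type I error, τ = 1.0 |
|---|---|---|---|
| 8 | 1 | 5.6% | 12.3% |
| 8 | 2 | 1.5% | 6.2% |
| 16 | 1 | 7.4% | 20.8% |
| 16 | 2 | 1.2% | 9.3% |

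A 10,000-replicate simulation gives 5.8%, 13.1%, 1.5%, 6.4%, 7.5%, 20.7%, 1.3% and 8.9%, in the same order.

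**One contrast per participant, one-sample t on 25 df.** 4.7–5.3% in the 20,000-replicate settings and 4.8–5.3% with omitted effects.

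**The case against.** A reader might infer that section 15.3 specifies an intercept-only model and that the primary tests therefore reject too often. The documents do not support that. The text names the grouping factor and is silent on slopes, so the intercept-only model is the natural literal reading, not a stated choice. Nor does any section say which coefficient is primary.

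The larger rates also need rows split by valence and task rule, neither of which is a listed predictor in 15.3. If such rows are stacked without those predictors, the omitted effects swell the residual, and the test can become conservative. Person-level variation in valence and rule effects works the same way: with SDs twice those for site and phase, the rates fall to about 5–6% with 8 rows and 7–10% with 16. With the four cells that 15.3 names, inflation is small or absent. The site-by-phase contrast, which isolates a DLPFC-specific phase effect, is conservative unless it varies between people and cells hold several rows. All of this stands, and it makes the size, and even the direction, of the error conditional.

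The post-hoc pairwise tests in 15.3 offer only partial cover. Paired on one value per person per condition, they would not depend on the mixed model's error term. However, 15.3 does not say they are paired, and it places them after the model.

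It would also go too far to say that findings could not extend beyond the 26 volunteers. No slope variance is given anywhere, and with none there is no inflation.

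**Conclusion.** The point holds in conditional form. Section 15.3 leaves the error term of the main behavioural comparison open, and its literal reading does not control the error rate. For the slope SDs assumed here, main-effect type I error runs from near 5% to about 28%, and it can drop to about 1% when large valence and rule effects are omitted. Inflation requires that site or phase effects really differ between people, and it is material only with more than one row per cell. The calculation ignores the shrinkage and dependence that a hierarchical diffusion model adds. I am confident about the missing specification and the remedy, but not about the size of any inflation. This is a cheap improvement, not an established error in the result.

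**What to change.** In 15.3, make the primary behavioural test one contrast per participant and parameter: peak minus trough in DLPFC blocks, the same in vertex blocks, and their difference. Test each with a one-sample t or sign-flip test on the 26 values. State which contrast is primary and how valence and task rule are averaged or separated.

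Equivalently, keep the mixed model but state the rows per participant and include valence and task rule wherever rows are split by them. Replace the single participant term with a random intercept plus by-participant slopes for site and phase, and for their interaction when cells hold more than one row.

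The cost is a change of wording, usually wider intervals, and fewer degrees of freedom (25 for a participant-level contrast). No data collection changes.

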- 5.1. Study Design: Up to 26 healthy adult volunteers will be recruited for participation in this randomized crossover study. The study will consist of up to three sessions – the first session using magnetic resonance imaging (MRI) session and subsequent sessions with transcranial magnetic stimulation and concurrent electroencephalography (TMS-EEG). Informed consent for all study procedures and initial questionaries will be obtained before the first session. The 3T MRI scan will provide accurate prefrontal cortex anatomy for using neuronavigation for TMS. During the TMS-EEG sessions, we will first identify individual TMS intensity of motor threshold by recording motor evoked potentials. The stimulation will then be applied with an intensity of up to 120% of the resting motor threshold (which is a safe and common practice; Rossi et al., 2021). The intensity can be decreased for individual participants. Two TMS-EEG conditions – verum and sham, will occur in intermittent blocks in randomized order, and

MEDICAL PROTOCOL (HRP-590)

PROTOCOL TITLE: Investigating the causal and phase-dependent role of prefrontal theta oscillations in approach/avoidance behavior

VERSION DATE: 14/09/2024

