lay in the supine position within the scanner and be asked to relax. T1 and T2-weighted images will be collected to provide anatomical models for neural navigation during TMS. In addition, diffusion tensor imaging will be collected to assess structural connectivity of the prefrontal cortex, and BOLD fMRI contrast will be collected during the resting state to assess functional connectivity. All imaging modalities will follow standard Human Connectome Project (HCP) protocols (Harms et al., 2018), as routinely used in CMRR. Overall scanning time will be under one hour.

- 5.2.3. The approach/avoidance (Ap/Av) test: In the Ap/Av task, during each task trial, the volunteer sees on the screen a human face with either positive emotion (happiness, joy), negative emotion (anger, fear), or neutral emotion (Figure 1). During the congruent condition, the volunteer has to pull a joystick towards themself when they see a face with positive emotions and push away when they see negative emotions. In the incongruent condition, the responses with a joystick are the opposite. Neutral emotional stimuli require no response. When a joystick is pulled, the image become larger on the screen (imitating approach), when a joystick is pushed away – it become smaller (imitating avoidance). The reaction times to the stimuli and reaction time difference between the congruent and incongruent conditions constitute the primary test outcomes. We will perform four task blocks (approx. ten minutes each): two with congruent conditions and two with incongruent. The emotional stimuli are taken from publicly available, scientifically validated databases of emotional facial expressions, including Karolinska Directed Emotional Faces (KDEF; Lundqvist et al., 1998) and AffectNet (Mollahosseini et al., 2017). All stimuli can legally be used and redistributed for research purposes. The task presentation PC will be synchronized with the EEG amplifier and TMS machine using TCP/IP, UDP, and/or TTL protocols. Total time per session is 4 blocks of approx. 10 minutes, with approx. 5 minutes breaks in between.

MEDICAL PROTOCOL (HRP-590)

PROTOCOL TITLE: Investigating the causal and phase-dependent role of prefrontal theta oscillations in approach/avoidance behavior

VERSION DATE: 14/09/2024

[figure not shown]

Figure 1. Overview of a single experimental TMS-EEG session.

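### The 15.3 model has no block-order term, so any practice, fatigue or rule-switch effect widens the standard errors of the between-block contrasts; the recorded sequence allows a cheap adjustment

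*Combined protocol and SAP*

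**What the plan says.** Section 5.1 plans "8 main blocks of approach/avoidance tasks with TMS (approx. 6 minutes per block) in randomized order", and says that the verum and sham conditions "will occur in intermittent blocks in randomized order". Before these, "volunteers will first perform a task training and a short (approx. 5 min) block of the approach/avoidance task (Ap/Av) without TMS". Between them, "There will be 3-5 min breaks in-between the blocks for rest". Section 5.2.5 repeats the figure of eight six-minute blocks per session. Section 5.2.3 differs: "We will perform four task blocks (approx. ten minutes each): two with congruent conditions and two with incongruent".

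Two things change from block to block. The coil is over the left DLPFC or the vertex (5.1, 5.2.5), and the response rule reverses (5.2.3: "In the incongruent condition, the responses with a joystick are the opposite").

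Section 15.1 turns reaction times into hierarchical drift-diffusion (HDDM) parameters. Section 15.3 compares these in a mixed model with "stimulation conditions (real vs control and peaks vs trough) as categorical independent variables, and participant IDs as a nuance variable", followed by pairwise nonparametric tests. Neither section has a term for block position, preceding block or session, and no section describes a counterbalancing scheme. Section 18.3 says that each participant's sequence is kept in an electronic file.

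**The concern.** Performance on a speeded task may change over a long session through practice or fatigue, and reversing the joystick rule may carry a switching cost. If each combination of site, phase and rule gets one block, a participant's peak and trough blocks will usually differ in average position. Any order effect then becomes part of that participant's contrast. With only participant and stimulation condition in the model, it is counted as residual noise. The noise handling that 15.1 attributes to HDDM is at trial level and does not remove a shift in a whole block's parameters.

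What is at stake is precision on the phase and site-by-phase comparisons in a study of 26 people. In addition, nothing planned would show whether a DLPFC block affects the block after it.

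**Working it through.** Below, trend means change over blocks, not the HDDM drift rate.

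**Inputs.** From the documents: 8 blocks in randomised order (5.1, 5.2.5), n = 26 and d = 0.5 (15.2), and the model terms (15.3). Not given: alpha, sidedness, target power, the contrast to which d refers, any block-level variance, any order effect. Assumed: one block per site × phase × rule cell (2 × 2 × 2 = 8, inferred), unrestricted random order, block-residual SD of 1, and a linear trend common to everyone, totalling T residual SDs from first to last block.

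**The plan's own figure.** For a paired comparison, n = ((z_alpha + z_power)/d)².
- One-sided 5%, 80% power: ((1.645 + 0.842)/0.5)² = 24.7, so 25 (exact t: 27). Power at 26 is 79.8%.
- Two-sided 5%, 80% power: ((1.960 + 0.842)/0.5)² = 31.4, so 32 (exact t: 34). Power at 26 is 68.8%.

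The plan does not say which it used. I take the two-sided test as the reference.

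**Exposure of each contrast.** Positions 1 to 8 have sum of squares 42 about their mean, so variance 42/7 = 6.
- Peak minus trough (4 v 4 blocks): position variance 6 × (1/4 + 1/4) = 3, SD 1.73 blocks; residual variance 1 × (1/4 + 1/4) = 0.5.
- Site-by-phase (four means of 2 blocks): position variance 6 × 4 × 1/2 = 12, SD 3.46 blocks; residual variance 4 × 1/2 = 2.

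The ratio is 6 both times (3/0.5 and 12/2). With slope b = T/7, the SE of either contrast is multiplied by √(1 + 6b²).

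**Power at n = 26, d = 0.5, paired t, no order term.**

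| T (block SDs) | SE factor | Effective d | Two-sided 5% | One-sided 5% |
|---|---|---|---|---|
| 0 | 1.000 | 0.500 | 68.8% | 79.8% |
| 0.5 | 1.015 | 0.493 | 67.5% | 78.7% |
| 1 | 1.059 | 0.472 | 63.8% | 75.7% |
| 2 | 1.221 | 0.410 | 51.9% | 65.1% |
| 3 | 1.450 | 0.345 | 39.4% | 52.6% |

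**What adjustment recovers.** Simulation with 26 participants, a fresh random order for each and 1,500 runs per setting. The larger model adds seven position indicators and a rule-switch indicator. Both models also contain congruency and the site-by-phase interaction, which 15.3 does not list. Two-sided power for phase:

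| Trend T; switch cost (SDs) | Without order terms | With order terms |
|---|---|---|
| 0; 0 | 72% | 70% |
| 1; 0 | 66% | 70% |
| 1; 0.5 | 62% | 71% |
| 2; 0.5 | 50% | 68% |
| 3; 1 | 34% | 70% |

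The starting value exceeds 68.8% because the residual is pooled over 208 − 30 = 178 degrees of freedom instead of 25. Bias was near zero and type I error was 4-5% with and without the terms.

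**If the trend differs between people.** Take a mean slope of 0.4 contrast SDs per block (0.4 × √0.5 × 7 = 1.98 block SDs in total) and a between-person SD of 0.4. On this scale 6b² becomes 3t², with t the slope in contrast SDs. Without the term the factor is √(1 + 3(0.16 + 0.16)) = 1.40 and power is 42%. With it, the factor is √(1 + 3 × 0.16) = 1.217 and power is 52%.

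**Preceding block.** Under random order of eight distinct cells, a vertex block follows a DLPFC block with probability 7/8 × 4/7 = 50%, and a DLPFC block does so with probability 7/8 × 3/7 = 37.5%. An after-effect of size c would shift the site contrast by c/8.

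**The case against.** The case against acting is substantial. Randomised order already protects validity, as the simulation shows. Training and a practice block come first and should blunt early learning, and rest breaks should limit fatigue. No trend, switch cost or variance is documented, so the loss could be 1 point of power or 20. The d of 0.5 comes from comparable studies and may already contain order noise, in which case part of the loss is counted. A common position term fitted to a common simulated trend is a best case. The GLMM outcome is an HDDM parameter: if that is estimated per condition, each estimate pools blocks and has no single position.

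All of this stands, and it limits the size of the point and shapes the fix. It does not remove the omission, since training does not address fatigue or rule reversal.

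Three stronger readings are tempting and unsupported:
- *The blocks run without pause.* Section 5.1 provides breaks.
- *The contrasts are biased by a trend, or the tests invalid.* Random order prevents this.
- *Site-by-phase is twice as exposed, because 3.46 is twice 1.73.* Its own residual SD doubles as well (√2 against √0.5), so the relative loss is equal.

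**Conclusion.** The point holds as a cheap gain in precision, not as an error that invalidates the analysis. That 15.3 omits block order is certain. How much this costs cannot be determined from the documents: the SE rises about 1.5% for a total trend of 0.5 block SDs, 6% for 1, 22% for 2 and 45% for 3. These figures rest on one block per cell, unrestricted random order and a shared linear trend. The asymmetry favours adjusting: about 0-2 points of power are lost if there is no order effect, and more is regained if there is a sizeable one. The two-sided reference of 68.8% leaves little precision to give away.

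The c/8 shift from an after-effect is the one component that random order does not remove. It concerns the site contrast only, is small, and calls for a check.

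**What to change.** 1. In 15.1, estimate the HDDM parameters per block, or enter order as HDDM regressors. In 15.3, add block position as a covariate from the stored sequence, and session if there is more than one TMS-EEG session (5.1 allows up to three visits and 5.3 expects three, the first for MRI).
2. Take the condition contrasts from this adjusted model. The pairwise nonparametric tests cannot carry covariates.
3. Pre-specify a sensitivity analysis with preceding-block site and rule switch.
4. Reconcile the block count and length in 5.1 and 5.2.5 with 5.2.3, and state how order is generated.
5. Then use position-balanced sequences for participants not yet randomised. If the count is eight, a Williams set has 8 sequences, so 24 of 26 participants are fully balanced and 2 are extra. Keep the position term, because balance alone leaves the trend in the residual. Keep the preceding-block analysis too, because such a set preserves the 50% and 37.5% proportions.

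The cost is some modelling work, noisier block-level HDDM estimates and a few degrees of freedom. The sequence is already recorded, and fixing the covariates before analysis avoids a post-hoc choice.

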- 2.2. Preliminary Data: We have developed a real-time TMS-EEG system which can continuously monitor the prefrontal theta rhythm (3-7 Hz) and trigger TMS pulses at specific phases with high accuracy. Our system has been validated in computational simulations and in proof-of-concept study in

MEDICAL PROTOCOL (HRP-590)

PROTOCOL TITLE: Investigating the causal and phase-dependent role of prefrontal theta oscillations in approach/avoidance behavior

VERSION DATE: 14/09/2024

healthy adults (Shirinpour et al., 2020). Recently, our real-time TMS-EEG system was used to investigate the phase-specific role of ongoing oscillations in motor cortex in adult participants, demonstrating robust performance and no unexpected side effects (Wischnewski et al., 2022).

- 2.3. Existing Literature: The combined application of TMS and EEG has established itself as a potent tool to probe and measure the causality of brain activity. It allows to accurately capture brain responses to the perturbation at specific times relative to the ongoing brain processes or cognitive tasks (Rogasch et al., 2016; Rogasch and Fitzgerald, 2013; Zrenner et al., 2016). Further, several recent studies have investigated the brain neurophysiology using real-time TMS-EEG for probing neural oscillations at different phases (Shirinpour et al., 2020; Schaworonkow et al., 2018; Zrenner et al., 2017). Our lab developed a novel closed-loop algorithm with higher accuracy compared to previous methods (Shirinpour et al., 2020). We recently applied the novel system to test the role of ongoing beta and mu oscillations in the motor cortex in healthy adults (Wischnewski et al., 2022). Moreover, the initial efforts to utilize real-time TMS-EEG for probing prefrontal activity and link between the prefrontal theta and cognition showed effectiveness and safety of such approach (Gordon et al., 2022).

3. Study Endpoints/Events/Outcomes

- 3.1. Primary Endpoint/Event/Outcome: The approach/avoidance test measures (reaction times to positive and negative emotional stimuli) during concurrent probing of ongoing prefrontal theta oscillations at peaks vs. troughs using TMS.
- 3.2. Secondary Endpoint(s)/Event(s)/Outcome(s): TMS-evoked potentials (TEPs) in concurrent EEG during the approach/avoidance test.

4. Study Intervention(s)/Investigational Agent(s)

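### One cluster-based permutation test is named for both TEP latency and TEP magnitude, and no latency measure is defined; run on the waveform, that test supports neither conclusion by itself

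*Combined protocol and SAP*

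**What the plan says.** TEPs are the secondary endpoint; section 3.2 gives it as "TMS-evoked potentials (TEPs) in concurrent EEG during the approach/avoidance test", without naming latency or any component. Section 15.1 describes cleaning the EEG, cutting it into segments time-locked to the stimulation, and then the step to "calculate the TMS-evoked potentials in the left DLPFC caused by the stimulation at the peak and trough of theta oscillations". It gives no component, search window, electrode set or definition of latency or magnitude.

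Section 15.3 supplies the inference: "Latency and magnitude of TMS-evoked potentials (TEPs) will be compared between the conditions using nonparametric cluster-based permutation test". On multiplicity, that section says only that this is done "with false discovery rate correction for number of comparisons". It does not say what the test takes as input (the voltage waveform or extracted values), whether clustering is over time or over electrodes, or what the comparisons being corrected are. It then adds: "Outcomes of TEPs and behavioral analysis will be correlated using Spearman statistics". The TEP quantity to be correlated is not defined.

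**The concern.** Latency and magnitude are different features of an evoked response. One is when a peak occurs and the other is how large it is. A cluster-based test on a voltage time course has a single global null hypothesis, that the conditions do not differ. Its error control attaches to that statement, not to the timing or size of any component, nor to where a cluster starts and ends.

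With one such test assigned to both features, a pure amplitude effect of theta phase could be reported as a latency effect, and a pure latency shift as a magnitude effect. The gap also reaches the correlation with behaviour, which needs one defined TEP value per participant.

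**Working it through.** **1. The plan's own figure.** Section 15.2 says "We estimated that medium effect size of Cohen's $d = 0.5$, which was observed in comparable studies" and "will be reached with a sample size of 26 volunteers"; section 5.1 gives the design: "Up to 26 healthy adult volunteers will be recruited for participation in this randomized crossover study". For a paired comparison, n = ((z_alpha + z_power)/d)².
- Two-sided 5%, 80% power: ((1.960 + 0.842)/0.5)² = 31.4, so 32 (34 with the t distribution).
- One-sided 5%, 80% power: ((1.645 + 0.842)/0.5)² = 24.7, so 25 (27 with the t distribution).

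Section 15.2 states no alpha, sidedness or power, so 26 has no unique reproduction; it lies closest to the one-sided case. It is not tied to TEP latency and the point does not depend on it. It is used below only as the number of simulated participants.

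**2. What a waveform test responds to.** Let f(t) be the TEP in one condition. Multiplying it by (1 + δ) gives a mean difference of δ·f(t). Shifting it by τ gives f(t − τ) − f(t), approximately −τ·f′(t). Both are non-zero, so both violate the null. For one Gaussian peak of height 4 (arbitrary units) and SD 18 ms:
- δ = 20%: largest difference 0.20 × 4 = 0.80, at the peak.
- τ = 5 ms: largest difference about 5 × (4/18) × e^(−0.5) = 5 × 0.222 × 0.607 = 0.67, on the flanks 18 ms either side of the peak.

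The two causes give differences of similar size.

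**3. Simulation.** Every waveform and noise value is an assumption; none is in the documents.
- Set A: 26 participants; a negative peak at 100 ms (SD 18 ms) and a positive peak at 180 ms (SD 25 ms, 0.9 of the height); participant amplitude mean 4, SD 1; participant latency SD 6 ms; smoothed noise SD 0.8. The cluster-mass test over time used a forming threshold of two-sided p < 0.05 and 200 sign flips, on 300 data sets per scenario. The latency test took the minimum between 60 and 140 ms with 999 sign flips, on 2,000 data sets.
- Set B: 26 participants, 5 µV peak, noise SD 1.4 µV per participant average, 200 sign flips for the cluster test, 200 data sets.

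| True difference | Set | Cluster test on waveform rejects | Test on extracted peak latency rejects |
|---|---|---|---|
| None | A | 6% | 4.3% |
| Amplitude +20%, no shift | A | 92% | 4.5% |
| Shift 5 ms, same amplitude | A | 80% | 82% |
| None | B | 3% | 6% |
| Amplitude +30%, no shift | B | 92.5% | 5.5% |
| Shift 6 ms, same amplitude | B | 77.5% | not computed |

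In set A the latency test also rejected in 3.8% for amplitude +30% and in 98% for an 8 ms shift. Monte Carlo standard errors: √(0.92 × 0.08/300) = 1.6 points, √(0.80 × 0.20/300) = 2.3 points, √(0.045 × 0.955/2000) = 0.5 points. The number of significant clusters per significant data set does not separate the causes clearly either: 1.58 on average for the amplitude change and 1.40 for the shift.

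**4. Which reading fits the text.** Section 15.1 stops at a TEP for one region, with no extraction step. One latency per participant and condition in one region would leave nothing to cluster over. Time is therefore the natural clustering dimension, and steps 2 and 3 apply to that reading.

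**The case against.** The strongest reply is that the test input is not stated. A reader might infer that a cluster-based test cannot address latency at all, and so that the latency outcome has no valid test. The documents do not support that. Section 15.3 names latency and magnitude as separate quantities. The recording is multichannel, since section 15.1 repairs noisy channels by interpolation. A false discovery rate correction fits a set of several tests. If latencies were extracted per participant and electrode and clustered over neighbouring electrodes, a permutation test would address latency validly. This part of the objection stands, and it makes the point conditional. It does not remove the point: the reader must supply the extraction step, and even then component, window, electrodes and estimator would remain open until the data had been seen.

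A second reply is that the simulation assumes waveform input and so shows what is true by construction. That is fair. It illustrates non-specificity under stated assumptions. It does not show which input the trial will use, and its rates are not the trial's error rates.

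A third reply is that little depends on latency. It appears only in section 15.3, not in objective 1.1.2 or endpoint 3.2, and a waveform test does answer whether TEPs differ between peak and trough. That also stands and limits the weight of the point. Nor do the documents say that latency will be read from a cluster's onset or extent, so it would be too strong to say that the endpoint will be misinterpreted.

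**Conclusion.** The point holds as a conditional one about specification and choice of test. As written, the latency comparison cannot be carried out without decisions the plan does not make. Carried out in the usual way, it would not separate latency from magnitude.

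The ambiguity runs in both directions, so calling the waveform cluster test an amplitude test would not cure it: a pure shift of 5 to 6 ms made it significant in 77.5% to 80% of simulated data sets. A test on extracted latency rejected in 3.8% to 5.5% under pure amplitude changes. These rates rest on assumed waveforms and noise; the non-specificity of the waveform test does not.

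The effect is confined to the secondary endpoint and to the correlation of TEPs with behaviour. It should be settled before the EEG data are analysed.

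**What to change.** 1. Keep the cluster-based test, and restrict its conclusion to whether TEP waveforms differ between the named conditions. Draw no latency or magnitude inference from a cluster's onset, extent or position.
2. Pre-set the components, their time windows, the left-DLPFC electrodes and the time zero, since section 5.1 allows up to three pulses per burst.
3. Extract one latency and one magnitude per participant, condition and component: for example peak or fractional-area latency, and peak or mean amplitude. State what is done when a component cannot be identified.
4. Compare each measure with its own paired permutation test, such as sign-flipping the within-participant differences.
5. Apply the false discovery rate correction across the named list of contrasts and components.
6. Use the same extracted values in the Spearman correlation with behaviour.

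The cost is SAP wording, a short extra script and a commitment to windows in advance. No new data or participant time is needed.
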